8.4.3 Analytic Plan for Correlative Endpoints

Lesion-specific response rate by baseline PSMA avidity on ⁶⁸Ga-PSMA-11 PET:

All target lesions on baseline cross-sectional imaging will be assessed for response (e.g. > 30% reduction in longest diameter) on subsequent imaging during the course of study. The median baseline uptake on Ga-PSMA-11 PET between responding versus non-responding lesions will be compared using Mann-Whitney test. In addition, Spearman's rank correlation will be used to compare baseline lesion uptake on Ga-PSMA-11 PET with percent change from baseline in longest tumor diameter on subsequent cross-sectional imaging on study.

Percent change from baseline in T cell repertoire, circulating T cell subsets, tumor infiltrating lymphocytes, and tumor PD-L1 expression by immunohistochemistry after one priming dose of Lu-PSMA RLT:

T cell repertoire will be estimated using Morasita's distance as previously described. Quantification of circulating T cell subsets and TILs will be performed using flow cytometry and immunohistochemical analysis of tumor tissue and whole blood, respectively. PD-L1 expression will be analyzed as the percentage of tumor cells with positive surface expression. Correlative testing may be performed at outside laboratory facilities (i.e. Strata Oncology). The percent change from baseline in these parameters will be reported using descriptive statistics (e.g. median, range, standard deviation). In an exploratory fashion, the study cohort will be dichotomized by those with percent change from baseline above and below median and efficacy outcomes will be compared between dichotomized subgroups using log-rank test for time-to-event endpoints (e.g. rPFS, duration of response) and Fisher's exact test for categorical variables (e.g. objective response rate, 6-month rPFS rate, PSA50 response rate).

Genomic Sequencing

We will utilize only CLIA-certified laboratories (e.g. Strata Oncology) to identify genetic mutations within mCRPC tumors to provide genetic information that can be returned to patient to potentially inform treatment decisions. Certain genomic sequencing will be performed by Strata Oncology. Strata Oncology is a precision oncology company that utilizes the StrataNGS assay, which is a 90-gene targeted assay that detects actionable genetic alterations (standard of care markers and clinical trial eligibility markers). The assay sequences DNA and RNA from FFPE slides or blocks for specific single nucleotide variants, multi-nucleotide variants, small insertions and deletions, gene fusions, exon skipping mutations, copy number changes, and de novo deleterious mutations in tumor suppressor genes. The StrataNGS assay will also measure expression levels for some immuno-oncology biomarkers that are not yet reported clinically, this data will be available to Strata for correlative analyses and future test expansion.

Tests are ordered online by physicians through a secure Physician Portal, and the patient's leftover tumor material is shipped to the laboratory (e.g. Strata Oncology) for testing. Positive and negative genomic alterations are reported and associated FDA-approved therapies and clinical trials are noted. The UCSF treating physician will discuss the results with the patient (including matched drug trials and approved therapies). Participant information (name, DOB, MRN, subject ID) will be provided to the testing laboratory to ensure that patients continue to have access to their genetic sequencing data should they decide to seek care elsewhere besides UCSF. Laboratories performing testing will not contact patients at any point during or

after study participation. Sample blocks sent to the testing laboratories will be returned to UCSF and will not be stored at these laboratories for future testing. Consenting to participate in this study does not enroll the participant in Strata's separate observational study – The Strata Trial (NCT03061305). Participants would need to sign a separate consent form for Strata Oncology to use the data for any other purpose other than what is specified in this protocol.

Association Between Tumor Dosimetry with Response

Patients will undergo optional SPECT/CT dosimetry scan on C1D2, approximately 24 hours after completion of priming dose of 177Lu-PSMA-617. The median tumor dosimetry on SPECT/CT between responding versus non-responding lesions will be compared using Mann-Whitney test. In addition, Spearman's rank correlation will be used to compare tumor dosimetry on SPECT/CT with percent change from baseline in longest tumor diameter on subsequent cross-sectional imaging on study.

9 Study Management

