2.1 Objectives

Primary Objectives

Part A: To determine the recommended phase 2 dose and schedule of ¹⁷⁷Lu-PSMA-617 in combination with pembrolizumab in patients with mCRPC.

Part B (Dose Expansion): To determine the objective response rate by RECIST 1.1 criteria.

Secondary Objectives

1. To characterize the safety profile of the combination.
2. To determine the median duration of response by RECIST 1.1 criteria.
3. To determine the proportion of patients who experience $\geq 50\%$ decline from baseline in serum PSA.
4. To determine the median PSA progression-free survival.
5. To determine the median time to symptomatic skeletal related event.
6. To determine the 6 month radiographic progression-free survival rate and median radiographic progression-free survival.
7. To determine the median overall survival.

Correlative Objectives

1. To assess the lesion-specific response rate by baseline PSMA avidity on ⁶⁸Ga-PSMA-11 PET.
2. To quantify the change from baseline in T cell repertoire, circulating T cell subsets, tumor infiltrating lymphocytes, and tumor PD-L1 expression by immunohistochemistry after one priming dose of Lu-PSMA RLT.
3. To explore the relationship between timing of the ¹⁷⁷Lu-PSMA-617 priming dose with initiation of pembrolizumab with respect to immunologic, safety, and efficacy outcomes.
4. To descriptively characterize the patterns of uptake on ⁶⁸Ga-PSMA-11 PET at the time of disease progression.
5. To explore relationship between tumor genomic profile with clinical outcomes including response rate and progression-free survival.
6. To explore the relationship between tumor dosimetry with objective response.

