⁷ Tumor biopsy will be performed during Screening and within 7 days preceding C2D1 visit. Screening biopsy must be performed prior to initiation of study treatment but is not subject to 28-day screening window. Bone biopsies are acceptable if no soft tissue lesion is amenable for biopsy. The same lesion should be selected for the follow up biopsy whenever feasible.

⁸ Whole blood (40 mL in Na-Heparin green top tube) will be collected on C1D1 (pre-dose), C2D1 (pre-dose), C3D1 (pre-dose), on Day 1 of every 3 cycles thereafter (e.g. C6D1, C9D1, etc), and at the time of disease progression

⁹ SPECT/CT dosimetry scan is optional.

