7.1 Measurable disease/ Target lesions

All measurable lesions (lesions that can be accurately measured in at least one dimension [longest diameter to be recorded] as ≥ 10 mm with spiral CT) up to a maximum of 2 lesions per organ and 5 lesions total, representative of all involved organs, should be identified as target lesions and recorded and measured at baseline. Target lesions should be selected on the basis of their size (lesions with the longest diameter) and the suitability for accurate repeated measurements (either by imaging techniques or clinically). A sum of the longest diameter (LD) for all target lesions will be calculated and reported as the baseline sum LD. The baseline sum LD will be used as a reference by which to characterize the objective tumor response.

Lymph node metastases must measure 1.5 cm or greater in short axis diameter to be considered target lesions, while other target lesions must measure 1 cm or greater (with spiral CT scans).¹⁷

Complete Response (CR):	Disappearance of all target lesions
Partial Response (PR):	At least a 30% decrease in the sum of the longest diameter (LD) of target lesions, taking as reference the baseline sum LD
Progressive Disease (PD):	At least a 20% increase in the sum of the LD of target lesions, taking as reference the smallest sum LD recorded since the treatment started (including baseline LD), or the appearance of one or more new lesions
Stable Disease (SD):	Neither sufficient shrinkage to qualify for PR nor sufficient increase to qualify for PD, taking as reference the smallest sum LD since the treatment started (including

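### The lesion-level uptake and dosimetry tests treat lesions from one patient as independent, so their p-values are too small if uptake (or dose) and shrinkage both cluster within patient

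*Combined protocol and SAP*

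**What the plan says.** For correlative objective 1, Section 8.4.3 takes the lesion as the unit: "All target lesions on baseline cross-sectional imaging will be assessed for response". Two tests follow. The first is a two-group comparison: "The median baseline uptake on Ga-PSMA-11 PET between responding versus non-responding lesions will be compared using Mann-Whitney test". The second is Spearman's "rank correlation will be used to compare baseline lesion uptake on Ga-PSMA-11 PET with percent change from baseline in longest tumor diameter". Section 7.1 sets how many lesions a patient can contribute: "up to a maximum of 2 lesions per organ and 5 lesions total".

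The dosimetry part of Section 8.4.3 repeats the first test: "The median tumor dosimetry on SPECT/CT between responding versus non-responding lesions will be compared using Mann-Whitney test". It also plans a Spearman correlation of dosimetry with change in diameter, without saying whether the unit is the lesion or the patient. Correlative objective 6 in Section 2.1 is worded for a patient-level outcome: "To explore the relationship between tumor dosimetry with objective response". The scan is not mandatory: "Patients will undergo optional SPECT/CT dosimetry scan on C1D2", and footnote 9 of the Schedule 1 calendar (Section 5.2) confirms "SPECT/CT dosimetry scan is optional".

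No section mentions a mixed model, GEE, a clustered rank test, permutation or resampling of patients, or a per-patient summary. No significance level, lesion count or ICC is given for these tests.

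**The concern.** The ordinary Mann-Whitney and Spearman tests take their null variance from independent observations. Lesions in one patient share tumour biology, one administered activity and one pembrolizumab exposure, so a patient with high uptake in one lesion may have high uptake in the others, and the same may hold for shrinkage. Five such lesions carry less information than five lesions from five patients, but the tests count them equally. A patient with five target lesions also weighs five times as much as a patient with one.

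The bias has a condition. If only one of the two variables is correlated within patients, the tests keep their level. Both must cluster before the p-values become too small.

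At stake is the reading of correlative objective 1, and of objective 6 as analysed by lesion. An apparent link between uptake or dose and response could be a chance finding more often than a conventional 5% implies, and could then influence patient selection or dosing hypotheses in later work.

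**Working it through.** The plan states no error rate for these tests, so there is no figure to reproduce. The check asks how often a nominal two-sided 5% test rejects when uptake and shrinkage are truly unrelated.

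**Inputs from the documents.** Patients: 43 at most (synopsis: about 18 in Part A and 25 in Part B). Target lesions per patient: 1 to 5 (Section 7.1; measurable disease is inclusion criterion 14). Patients with dosimetry: unknown, because the scan is optional.

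**Assumed inputs.** ICCs from 0 to 0.7; lesion counts of 1–2, 1–5 or five each; 45% of lesions responding; 12 or 20 patients scanned.

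**Approximation.** With *m* lesions per patient, ignoring the patient understates the null variance by the factor

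1 + (*m* − 1) × ICC(uptake) × ICC(shrinkage),

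and the real size is 2 × [1 − Φ(1.96 / √factor)]. For *m* = 5:

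- ICC 0.1 in both: 1 + 4 × 0.01 = 1.04, size 5.5%
- ICC 0.2: 1 + 4 × 0.04 = 1.16, size 6.9%
- ICC 0.3: 1 + 4 × 0.09 = 1.36, size 9.3%
- ICC 0.5: 1 + 4 × 0.25 = 2.00, size 16.6%
- ICC 0.7: 1 + 4 × 0.49 = 2.96, size 25.5%
- One ICC equal to zero: factor 1, size 5%

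The product of the ICCs shows why both variables must cluster.

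**Simulation.** 6,000 null trials per setting, normal patient effects drawn independently for the two variables. The Monte Carlo standard error near 5% is √(0.05 × 0.95 / 6,000) ≈ 0.3 points. Real size at ICC 0.3 / 0.5 / 0.7 in both variables:

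| Patients | Lesions each | Mann-Whitney | Spearman |
|---|---|---|---|
| 43 | 1–2 | 5.9 / 5.9 / 8.2% | 6.2 / 6.7 / 9.0% |
| 43 | 1–5 | 6.4 / 10.2 / 15.6% | 7.1 / 12.5 / 19.6% |
| 43 | 5 | 7.4 / 12.1 / 20.2% | 8.6 / 15.2 / 24.7% |
| 20 | 1–5 | 6.9 / 9.4 / 15.5% | 7.9 / 11.9 / 18.9% |
| 12 | 1–5 | 5.9 / 9.4 / 14.3% | 7.2 / 11.4 / 18.0% |

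With unequal ICCs (0.3 for uptake, 0.7 for shrinkage; 43 patients, 1–5 lesions) the sizes are 9.5% and 11.7%. With only one variable clustered, at ICC 0.5 or 0.7, they stay between 4.3% and 5.6% for all lesion counts.

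A second simulation (3,000 trials, 40% of lesions responding) agrees. For 43 patients with five lesions each it gives Mann-Whitney 7.7 / 12.6 / 19.4% and Spearman 10.1 / 16.5 / 24.8%.

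**Do the remedies hold their level?** With 1–5 lesions and the same ICCs:

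- Whole-patient permutation: Mann-Whitney 4.6–5.1% and Spearman 4.8–5.1% with 43 patients; 5.2–5.5% and 5.2–5.7% with 20; 4.5–5.5% and 5.3–6.1% with 12.
- Spearman on patient means: 4.6–6.1%.
- A clustered rank-sum test: 5–6%, down to 12 patients.
- Rank regression with patient-clustered standard errors is less safe when patients are few. In the second simulation it reached 7.3% with 25 patients and 8.6% with 15.

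**The case against.** The strongest reply concerns weight and size. These are correlative objectives. The sample size in Section 8.1 does not rest on them, no decision depends on their p-values, and the plan assigns them no significance level, so the 5% used here is a convention and not a promise of the protocol. All of that stands, and it limits the importance of the point.

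The ICCs are not known either, and they may be low. Section 1.3 stresses how variable PSMA expression is, which may mean that uptake differs between lesions of one patient. At ICC 0.1 in both variables, simulation with 43 patients gives about 5% for both tests; at 0.2 with 1–5 lesions it gives 5.9% and 6.8%. Five target lesions need at least three involved organs, because each organ contributes at most two, and the documents do not say how common that is. The 20–25% figures are therefore an extreme case. This also stands.

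Against it, the trial's own rationale points to clustered shrinkage: Sections 1.3 and 1.5 expect an immune response that spreads to other lesions of the same patient. Section 1.3 also describes an earlier study that selected patients with more homogeneous uptake, which suggests that uptake patterns differ between patients. For dosimetry, all lesions of a patient share one administered activity, and Section 3.1 allows a second dose level for later patients. The reply lowers the likely size of the problem. It does not supply the missing allowance for the patient.

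**Conclusion.** The concern holds in its conditional form. Followed as written, Section 8.4.3 gives p-values that are too small whenever uptake (or dose) and shrinkage both correlate within patients and many patients have several target lesions. For 43 patients with 1–5 lesions, the real size of a nominal 5% test is about 6–16% (Mann-Whitney) and 7–20% (Spearman) over ICCs of 0.3 to 0.7. With 12 or 20 scanned patients it is about 6–16% and 7–19%. It is close to 5% if either ICC is near zero, if both are about 0.1, or if most patients have one target lesion.

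The ICCs, lesion counts, response proportion and number of scanned patients are assumptions; the missing adjustment is not. The consequence is confined to exploratory findings. The point is worth correcting because the correction is cheap, but it does not affect the primary or secondary results.

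**What to change.** State in Section 8.4.3 that the patient is the independent unit for both the PET and the dosimetry analyses.

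- **Preferred method.** Keep the Mann-Whitney and Spearman statistics on lesions, but take the p-value from permuting whole patients: exchange each patient's full set of uptake (or dose) values among patients with the same number of lesions. Give the Spearman coefficient an interval from a bootstrap that resamples patients.
- **Alternative for the responder comparison.** Use a clustered rank-sum test that allows responding and non-responding lesions in the same patient. It is useful when few patients share a lesion count and permutation has little to exchange.
- **If GEE or a mixed logistic model is used,** add a small-sample correction, because the optional scan may leave few patients.
- **Dosimetry.** Say that the unit is the target lesion clustered by patient, for both tests, and align the wording of objective 6 with it.
- **Reporting.** Give the number of patients and the distribution of lesions per patient for each analysis.

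The cost is a few sentences and a little more code, with no new data. Intervals will be somewhat wider. Spearman on patient means is valid but should be a fallback, because it gives up the within-patient comparison of lesions. With an assumed lesion-level slope of 0.5, 1–5 lesions and ICCs of 0.3–0.5 (300 trials), its power was 82–84% against 99% for whole-patient permutation with 43 patients, 48–49% against 74–81% with 20, and 27–28% against 47–51% with 12.

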Study Design	
This is a single-center Phase 1b open-label, study of PSMA-targeted radionuclide therapy with ^{177}Lu-PSMA-617 in combination with pembrolizumab in patients with mCRPC who have previously progressed on at least one prior androgen pathway inhibitor (e.g. abiraterone, enzalutamide, apalutamide). Patients must have at least three metastatic lesions which are PSMA-avid on baseline ^{68}Ga-PSMA-11 PET imaging.
 
In Part A of the study, patients will be enrolled sequentially into one of three treatment schedules with respect to timing of ^{177}Lu-PSMA-617 in relation to first dose of pembrolizumab (N = 6 patients per schedule):
 
Schedule 1) Priming dose of ^{177}Lu-PSMA-617 administered on Cycle 1 Day 1 followed by pembrolizumab 200 mg IV q 21 days starting Cycle 2 Day 1.
 
Schedule 2) Priming dose of ^{177}Lu-PSMA-617 administered concurrently with initiation of pembrolizumab on Cycle 1 Day 1.
 
Schedule 3) Priming dose of ^{177}Lu-PSMA-617 administered on Cycle 1 Day 1 following initiation of pembrolizumab on Cycle 1 Day -21.
 
The dose-limiting toxicity window will be Cycle 1 + Cycle 2 (i.e. 6 weeks following C1D1 administration of Lu-PSMA-617 across) in all three Schedule cohorts.
 
In Part A of the study, 6 patients will be enrolled to Schedule 1, then 6 patients to Schedule 2, and finally 6 patients will be enrolled to Schedule 3.
 
The starting dose of ^{177}Lu-PSMA-617 will be 7.4 +/- 15% GBq, which is the recommended phase 3 dose of the agent. If the DLT frequency attributable to Lu-PSMA exceeds 33% at any point after 6 evaluable patients have been enrolled in Part A, Dose Level -1 of ^{177}Lu-PSMA-617 will be investigated (4 Gbq +/- 15%) for the remainder of patients enrolled on study.
 
Using the data obtained in Part A, the recommended phase 2 dose and schedule of ^{177}Lu-PSMA-617 will be determined by the Principal Investigator using a combination of safety, efficacy, and immunologic effects of treatment from the first two cycles (and additional cycles of treatment when available).
 
In Part B of the study, an additional 25 patients will be enrolled at the recommended phase 2 dose and schedule to obtain additional safety, efficacy, and immunologic data pertaining to the treatment combination.

--------------	--

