Number of patients	
Approximately 18 patients will be enrolled during Part A of the study. An additional 25 patients will be enrolled in Part B.
 
Total sample size: 43
 
Part A: N ~ 18 patients (6 patients per Schedule; 3 Schedules to be evaluated)
 
Part B: N ~ 25 patients

Duration of Therapy	Patients will be treated until disease progression per PCWG3/RECIST 1.1 criteria, confirmed by repeat scans performed \geq 4 weeks later, unacceptable toxicity, or patient withdrawal, whichever occurs first.
Duration of Follow up	Patients will undergo safety follow up visit approximately 30 days and 90 days following end of treatment visit.
Duration of study	The study is anticipated to accrue 2-3 patients per month for an estimated accrual period of 21 months. The study is expected to reach completion for analysis of primary and secondary endpoints approximately 36 months from first patient enrolled.
Study Drugs	
¹⁷⁷Lu-PSMA-617 is a PSMA-targeted radioligand that will be produced under Current Good Manufacturing Practice (CGMP) regulations. The priming dose of ¹⁷⁷Lu-PSMA-617 will be 7.4 +/- 15% GBq, which is the recommended phase 3 dose of the agent.
 
The planned dose schedules to be evaluated in Part A of the study include:
 
Schedule 1) Priming dose of ¹⁷⁷Lu-PSMA-617 administered on Cycle 1 Day 1 followed by pembrolizumab 200 mg IV q 21 days starting Cycle 2 Day 1.
 
Schedule 2) Priming dose of ¹⁷⁷Lu-PSMA-617 administered concurrently with initiation of pembrolizumab on Cycle 1 Day 1.
 
Schedule 3) ¹⁷⁷Lu-PSMA-617 administered on Cycle 1 Day 1 following initiation of pembrolizumab on Cycle 1 Day -21.
 
The cumulative safety data, including safety data beyond Cycle 2 where available, immunologic priming effects, along with efficacy and pharmacodynamic data, will be utilized to determine the recommended schedule of ¹⁷⁷Lu-PSMA-617 in combination with pembrolizumab.

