⁷ Tumor biopsy will be performed during Screening and within 14 days preceding C3D1 visit. Screening biopsy must be performed prior to initiation of study treatment but is not subject to 28-day screening window. Bone biopsies are acceptable if no soft tissue lesion is amenable for biopsy. The same lesion should be selected for the follow up biopsy whenever feasible. PSMA-avid lesion should be prioritized for biopsy; non-PSMA avid lesion may be used if no PSMA-avid lesion is accessible.

⁸ Whole blood (40 mL in Na-Heparin green top tube) will be collected on C1D-21 (pre-dose), C1D1 (pre-dose), C2D1 (pre-dose), C3D1 (pre-dose), on Day 1 of every 3 cycles thereafter (e.g. C6D1, C9D1, etc), and at the time of disease progression.

⁹ SPECT/CT dosimetry scan is optional.

6 Reporting and Documentation of Results

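### Immune change labelled as following one Lu-PSMA dose is sampled after 0, 1 or 3 pembrolizumab doses depending on schedule (0, 1 or 2 for C2D1 blood), and the exploratory median split ignores schedule

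*Combined protocol and SAP*

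**What the plan says.** Correlative objective 2 (section 2.1) and section 8.4.3 name four immune measures: T-cell repertoire, circulating T-cell subsets, tumor-infiltrating lymphocytes and "tumor PD-L1 expression by immunohistochemistry after one priming dose of Lu-PSMA RLT". Section 8.4.3 reports percent change descriptively, without saying whether by schedule or overall. As an exploratory step, "the study cohort will be dichotomized by those with percent change from baseline above and below median", and efficacy is compared between the halves by log-rank and Fisher tests.

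The schedules differ in when pembrolizumab starts. Schedule 1 gives Lu-PSMA on C1D1 "followed by pembrolizumab 200 mg IV q 21 days starting Cycle 2 Day 1". Schedule 2 starts both on C1D1. Schedule 3 starts pembrolizumab on C1D-21, and its calendar (section 5.4) marks further infusions on C1D1 and from Cycle 2 on.

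For Schedules 1 and 2 the calendar footnote reads "Tumor biopsy will be performed during Screening and within 7 days preceding C2D1 visit". For Schedule 3 it reads "Tumor biopsy will be performed during Screening and within 14 days preceding C3D1 visit" and adds "PSMA-avid lesion should be prioritized for biopsy", a rule that the other two calendars lack. Blood is drawn pre-dose on C1D1, C2D1 and C3D1 in all schedules, and also on C1D-21 in Schedule 3.

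On schedule selection, the Study Drugs entry of the abstract says "immunologic priming effects, along with efficacy and pharmacodynamic data, will be utilized to determine the recommended schedule". The Study Design entry and section 3.1 likewise list immunologic effects alongside safety and efficacy. Section 8.4.1 names safety and efficacy only. Correlative objective 3 asks how timing relates to immunologic outcomes, but section 8.4.3 gives it no analysis.

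**The concern.** The label attributes the change to the radioligand, yet in two of the three schedules the follow-up sample is taken after pembrolizumab as well. The protocol itself recognises that checkpoint blockade can move one of these measures: section 1.6 reports that ipilimumab, a different checkpoint inhibitor, increased T-cell receptor diversity, with the repertoire still evolving over later months.

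Radioligand priming is the trial's central hypothesis. Section 1.7.1 justifies raising Part B from 12 to 25 patients partly by paired biopsies that may help to identify likely responders, and the median split is the analysis in section 8.4.3 that links immune change to outcome. If schedule influences which half a patient falls in, a difference in efficacy between schedules could be read as a biomarker effect. Immune data may also feed into schedule choice, and the biopsies are not taken on equal terms across the three schedules.

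**Working it through.** The plan gives no figure of its own here, so the check is a count from the calendars.

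**Inputs.** Lu-PSMA is day 0 (C1D1). Cycles last 21 days, so C2D1 is day 21 and C3D1 is day 42. This agrees with the two-cycle DLT window given in the abstract, "6 weeks following C1D1 administration of Lu-PSMA-617" (2 × 21 = 42 days). Pembrolizumab is given every 3 weeks (section 4). Biopsy and blood times come from footnotes 7 and 8 of sections 5.2 to 5.4. The counts assume nominal visit days and no held or delayed infusion.

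| | Schedule 1 | Schedule 2 | Schedule 3 |
|---|---|---|---|
| Pembrolizumab visits through C3D1 | C2D1, C3D1 | C1D1, C2D1, C3D1 | C1D-21, C1D1, C2D1, C3D1 |
| Follow-up biopsy, days after Lu-PSMA | 21 − 7 = 14 to 21 | 14 to 21 | 42 − 14 = 28 to 42 |
| Doses before biopsy | 0 | 1 | 3 |
| Doses before C2D1 blood (day 21) | 0 | 1 | 2 |
| Doses before C3D1 blood (day 42) | 1 | 2 | 3 |

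The biopsy rows apply to tumor-infiltrating lymphocytes and PD-L1. The blood rows apply to circulating subsets and, by assumption, to repertoire, which the plan does not assign to a sample. In Schedule 3 two blood draws precede Lu-PSMA and the plan does not say which is baseline. The interval to C2D1 contains 2 pembrolizumab doses if C1D-21 is used, and 1 if C1D1 is used.

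**Make-up of a pooled set of follow-up biopsies, if all patients contribute.**

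- Part A: pembrolizumab-free 6/18 = 33%; mean prior doses (6×0 + 6×1 + 6×3)/18 = 1.33.
- Part B on Schedule 1: pembrolizumab-free (6 + 25)/43 = 31/43 = 72%; mean (6×1 + 6×3)/43 = 0.56.
- Part B on Schedule 2: pembrolizumab-free 6/43 = 14%; mean (31×1 + 6×3)/43 = 1.14.
- Part B on Schedule 3: pembrolizumab-free 6/43 = 14%; mean (6×1 + 31×3)/43 = 2.30.

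**Illustration of the split.** Assume no Lu-PSMA effect at all and a shift of d standard deviations per pembrolizumab dose, with 6 patients per schedule (40,000 simulated Part A cohorts). These values of d are assumptions, not estimates. The expected pooled change is 1.33d.

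| d | Pooled mean change (SD) | Share above the pooled median, Schedules 1 / 2 / 3 |
|---|---|---|
| 0 | 0 | 50 / 50 / 50% |
| 0.25 | 0.33 | 37 / 47 / 66% |
| 0.5 | 0.67 | 25 / 44 / 81% |
| 1 | 1.33 | 11 / 42 / 96% |

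A pooled change appears although Lu-PSMA does nothing, and the split partly sorts patients by schedule.

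**What remains when schedules are separated.** For the Schedule 1 change with n = 6, the smallest two-sided exact paired p-value is 2 × 0.5^6 = 0.031. A median split in a single schedule of 6 gives 3 v 3, where the smallest two-sided Fisher p-value is 2/20 = 0.10. Testing each schedule alone is therefore close to uninformative, which favors splitting within schedule and combining the strata in one test.

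**The case against.** The strongest reply is that these are exploratory correlatives and that several harsher readings go beyond the text. Five of those readings are tempting, and the documents do not support them.

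- **The trial cannot show Lu-PSMA priming.** Schedule 1 biopsies and C2D1 blood precede any pembrolizumab, so a clean though small and uncontrolled estimate exists.
- **The schedules cannot be compared.** Schedules 1 and 2 share a biopsy window and all three share post-Lu-PSMA blood days. Different pembrolizumab exposure at a given time is part of the intended contrast between schedules.
- **All immune results will be pooled.** Pooling is explicit only for the median split. The descriptive summary is silent, and correlative objective 3 points towards looking by schedule.
- **Being above the median just means Schedule 3.** This is impossible in Part A, where 9 of 18 lie above the median and only 6 are in Schedule 3. Schedule can be associated with the split but cannot equal it.
- **The schedule will be picked on a sampling artefact.** Immune effects are one input among several, and section 8.4.1 does not list them at all.

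The lesion point also has limits. Every patient needs three PSMA-avid lesions, all calendars ask for the same lesion to be rebiopsied where feasible, and Schedule 3 allows a non-avid lesion when no avid one is accessible. What stands is that the priority rule is written for one schedule only.

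None of this removes the mismatch between the label and the Schedule 2 and 3 samples, or the absence of schedule from the split.

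**Conclusion.** The point holds in a limited form. Only Schedule 1 measures change after Lu-PSMA alone. Follow-up biopsies come after 0, 1 and 3 pembrolizumab doses, the last about 28-42 rather than 14-21 days after Lu-PSMA. C2D1 blood is matched in timing but follows 0, 1 and 2 doses. A change pooled across schedules cannot be attributed to Lu-PSMA, and the median split as written confounds immune change with schedule. How large the bias is depends on how far pembrolizumab moves each measure and on how outcome differs by schedule, which the documents do not give; the simulated shares show only a possible range. Schedule 3 tumor changes are not comparable with the others in timing or stated lesion rule.

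Because the endpoints are exploratory and the remedy is text, this should be corrected but does not threaten the primary analyses.

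**What to change.** In section 8.4.3:

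1. Report each immune change by schedule. Take the Lu-PSMA-only estimate from Schedule 1 (n = 6, or 31 if Part B uses Schedule 1), and label Schedule 2 and 3 changes as change after the combination.
2. Name the baseline and follow-up sample for each measure. In Schedule 3 blood, label C1D-21 to C1D1 as pembrolizumab alone, and C1D1 to C2D1 as Lu-PSMA plus a further pembrolizumab dose, since pembrolizumab is also infused on C1D1.
3. Make the median split within schedule and compare outcomes with schedule-stratified tests: a stratified log-rank test for time-to-event endpoints and an exact stratified test for proportions.
4. Where biopsy changes inform schedule choice, compare Schedules 1 and 2 directly, and state that Schedule 3 biopsies are not matched in timing or lesion rule.

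Also reconcile the abstract (Study Design and Study Drugs) and section 3.1 with section 8.4.1 on whether immunologic data inform schedule selection.

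No biopsy, blood draw or calendar change is needed, and the rules can be applied to samples already collected. The text change is a protocol amendment and needs the approvals in section 9.4. The statistical cost is a smaller n for the Lu-PSMA-only estimate and lower precision in the stratified exploratory tests.
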